4.1 Objectives

Primary objective

To confirm the superiority of liraglutide at the maximum tolerated dose (0.6 mg, 1.2 mg or 1.8 mg) versus placebo when added to metformin with or without basal insulin treatment in controlling glycaemia in children and adolescents (ages 10–17 years) with type 2 diabetes.

Secondary objectives

To assess and compare the effect of liraglutide versus placebo in combination with metformin with or without basal insulin treatment on:

- Parameters of glycaemic control
- Parameters of beta-cell function
- Parameters of body composition
- Vital signs
- Growth velocity (if subject is still growing)
- Safety and tolerability
- Growth and pubertal development at 1 and 2 year follow up after trial drug cessation at week 52

4.2 Endpoints

Primary endpoint to be assessed at 26 weeks of treatment

- Change in HbA_{1c} from baseline to week 26

Confirmatory secondary endpoints to be assessed at 26 weeks of treatment

- Change from baseline in FPG
- HbA_{1c} <7.0% (yes/no)
- Change from baseline in BMI standard deviation score (SDS)

Secondary endpoints to be assessed at 26 and 52 weeks of treatment unless otherwise stated

- HbA_{1c} <7.0% (yes/no) at 52 weeks
- HbA_{1c} ≤6.5% (yes/no)
- HbA_{1c} <7.0% without severe or minor hypoglycaemic episodes (yes/no)
- HbA_{1c} <7.5% (yes/no)

Change from baseline at 26 and 52 weeks of treatment unless otherwise stated:

- HbA_{1c} at 52 weeks
- FPG at 52 weeks
- 7-point self-measured plasma glucose (SMPG)
 - Mean 7-point SMPG
 - Post-prandial increments
- Fasting insulin, fasting pro-insulin, pro-insulin to insulin ratio, fasting glucagon, fasting C-peptide, and homeostasis model assessment (HOMA-B and HOMA-IR)
- Fasting lipid profile (cholesterol, low density lipoprotein (LDL), very low density lipoprotein (VLDL), high density lipoprotein (HDL), triglycerides and free fatty acids)
- Body weight
- Waist circumference
- Body mass index (BMI)
- BMI SDS at 52 weeks
- BMI percentile (age and gender adjusted)
- Systolic and diastolic blood pressure
- Basal insulin dose

Safety endpoints

Change from baseline at 26 and 52 weeks of treatment unless otherwise stated

- Clinical evaluations (physical examination including fundoscopy [fundoscopy at 26 and 52 weeks])
- Electrocardiography (ECG) with rhythm strip (at 26 and 52 weeks)
- Pulse
- Laboratory tests:
 - Haematology (haemoglobin, haematocrit, thrombocytes, erythrocytes, leucocytes and differential count (eosinophils, neutrophils, basophils, lymphocytes and monocytes))
 - Biochemistry (creatinine, creatine kinase, urea, albumin, bilirubins (total), alanine aminotransferase (ALAT), aspartate aminotransferase (ASAT), alkaline phosphatase, sodium, potassium, calcium, calcium (albumin corrected), amylase and lipase)
 - Hormones (calcitonin, prolactin, follicle stimulating hormone (FSH), estradiol, luteinizing hormone (LH), testosterone, dehydroepiandrosterone sulfate (DHEAS), carcinoembryonic antigen (CEA) and thyroid stimulating hormone (TSH), insulin-like growth factor 1 (IGF-1), insulin-like growth factor binding protein 3 (IGFBP-3))
 - First morning urinalysis (micro albumin, creatinine, albumin:creatinine ratio calculated, protein, ketone, glucose, pH)
 - Biochemical parameters of bone metabolism: Alkaline Phosphatase, N-telopeptide (NTX), C-telopeptide (CTX), serum type 1 procollagen (P1NP)
 - Formation of anti liraglutide antibodies (at 26 and 53 weeks)

- Height SDS
- Bone age assessment (x-ray of left hand and wrist) at 52 weeks
- Pubertal assessment/ progression (Tanner staging)

In addition the following will be assessed at 26, and 52 weeks:

- Assessment of compliance (questioning of subjects and subjects legally acceptable representative)
- Growth velocity in cm/year and height velocity SDS (if subject is still growing). A growth velocity < 1.0 cm/year is defined as no longer growing.
- Hypoglycaemic episodes
- AEs and serious adverse events (SAEs)

Safety follow-up at 1 and 2 years after trial drug cessation at week 52 (only applicable for subjects on active liraglutide treatment for more than 3 months)

- AEs and SAEs
- Growth velocity in cm/year (if subject is still growing)
- Height velocity SDS (if subject is still growing)

Change in:

- Height SDS
- Pubertal assessment/progression (Tanner staging)
- Bone Age assessment (x-ray of left hand and wrist)

5 Type of trial

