20. Human immunodeficiency virus (HIV) positive

21. Uncontrolled hypertension, treated or untreated >99th percentile for age and gender in children (see Appendix B). If “white coat hypertension” is suspected at Visit 1 a repeat blood pressure measurement either during Visit 1, or at Visit 2 prior to other trial related activities is allowed, with the last measurement being conclusive
22. Any history of or diagnosis/treatment of cancer within the last 5 years (except basal cell skin cancer or squamous cell skin cancer)
23. Any clinically significant disorder, except for conditions associated with type 2 diabetes history which in the investigator’s opinion could interfere with results of the trial
24. Surgery scheduled for the trial duration period (excluding minor surgical procedures performed in local anaesthesia, as judged by the investigator)
25. Recurrent severe hypoglycaemia or hypoglycaemic unawareness as judged by the investigator
26. Use of any drug (except for metformin and/or basal insulin), which in the Investigator’s opinion, could interfere with the blood glucose level (e.g. systemic corticosteroids)
27. Known or suspected abuse of alcohol or drugs/narcotics
28. Mental incapacity or language barrier precluding adequate understanding or cooperation or unwillingness to adhere to protocol requirements

Proportion of subjects above 14 years of age will be restricted to a total of 70% of randomised subjects (see section [5.1](#)). Proportion of male subjects will be restricted to a total of 60% of randomised subjects. When the individual target is reached, subjects above 14 years of age and male subjects respectively may not be randomised into the trial.

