8.7.7 Bone age assessment

An x-ray of left hand and wrist will be performed at Visits 7 and 25 for all subjects for evaluation of bone age. In addition subjects treated with liraglutide for more than three months will have an x-ray performed at Visits 27 and 28. A repeat bone age assessment will not be performed at subsequent visits (25, 27 or 28) for subjects for whom the bone age assessment at Visit 7, or at a later visit, indicates that the epiphyses are fused. The x-rays will be analysed by a central reader for determination of bone age. Further requirements and details will be described in the x-ray site manual.

An x-ray performed within 2 weeks prior to Visit 7, 25, 27 and 28 is acceptable.

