It is assumed that the risks and benefits associated with liraglutide treatment will be the same for the paediatric population as for the adult populations (see section [3.1.3](#)) with the exception of any unforeseen effects on growth and pubertal development.

When treatment with trial products ends, the subject and investigator will decide on the best available treatment for the subject. Novo Nordisk will not offer investigational drug(s) after the end of trial.

Subjects participating in the trial and their parents may be reimbursed for documented reasonable travelling expenses and loss of income, as according to local law. All agreements on compensation should be approved by the IRB/Ethical committee.

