2.2.3 Secondary safety endpoints

Change from baseline at 26 and 52 weeks of treatment unless otherwise stated

- Clinical evaluations (physical examination including fundoscopy [fundoscopy at 26 and 52 weeks])
- Electrocardiography (ECG) with rhythm strip (at 26 and 52 weeks)
- Pulse*
- Laboratory tests:
 - Haematology (haemoglobin, haematocrit, thrombocytes, erythrocytes, leucocytes and differential count (eosinophils, neutrophils, basophils, lymphocytes and monocytes)
 - Biochemistry (creatinine, creatine kinase, urea, albumin, bilirubins (total), alanine aminotransferase (ALAT), aspartate aminotransferase (ASAT), alkaline phosphatase, sodium, potassium, calcium, calcium (albumin corrected), amylase and lipase)
 - Hormones (calcitonin, prolactin, follicle stimulating hormone (FSH), estradiol, luteinizing hormone (LH), testosterone, dehydroepiandrosterone sulfate (DHEAS), carcinoembryonic antigen (CEA) and thyroid stimulating hormone (TSH), insulin-like growth factor 1 (IGF-1), insulin-like growth factor binding protein 3 (IGFBP-3)
 - First morning urinalysis (micro albumin, creatinine, albumin:creatinine ratio calculated, protein, ketone, glucose, pH)

Liraglutide
Trial ID: NN2211-3659
Statistical Analysis Plan
EurdraCT No.: 2011-002605-29

Date: 25 June 2018 Vovo Nordisk
Version: 2.0
Status: Final
Page: 10 of 25

- Biochemical parameters of bone metabolism: Alkaline Phosphatase, N-telopeptide (NTX), C-telopeptide (CTX), serum type 1 procollagen (P1NP)
- Formation of anti liraglutide antibodies (at 26 and 53 weeks)
- Height SDS*
- Bone age assessment (x-ray of left hand and wrist) at 52 weeks*
- Pubertal assessment/ progression (Tanner staging)*

In addition the following will be assessed at 26 and 52 weeks:

- Assessment of compliance (questioning of subjects and subjects legally acceptable representative)
- Growth (height) velocity in cm/year and height velocity SDS (if subject is still growing). A growth velocity < 1.0 cm/year is defined as no longer growing.*
- Hypoglycaemic episodes*
- AEs and serious adverse events (SAEs)*

Safety follow-up at 1 and 2 years after trial drug cessation at week 52 (only applicable for subjects on active liraglutide treatment for more than 3 months)

- AEs and SAEs*
- Growth (height) velocity in cm/year (if subject is still growing)*
- Height velocity SDS (if subject is still growing)

Change in:

- Height SDS
- Pubertal assessment/progression (Tanner staging)*

Liraglutide		Date:	25 June 2018	Novo Nordisk

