Trial ID: NN2211-3659	CONFIDENTIAL	Version:	2.0	
Statistical Analysis Plan	CONFIDENTIAL	Status:	Final	
EurdraCT No.: 2011-002605-29		Page:	11 of 25	

• Bone Age assessment (x-ray of left hand and wrist)*

^{*} Key secondary endpoint prospectively selected for disclosure (e.g. clinicaltrials.gov and EudraCT)

Liraglutide Trial ID: NN2211-3659 Statistical Analysis Plan EurdraCT No.: 2011-002605-29

CONFIDENTIAL

Date: Version: Status: Page:

25 June 2018 | Novo Nordisk 2.0 Final 12 of 25

3 Statistical considerations

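### Growth velocity is summarised only in children still growing, and that status is judged by the on-treatment velocity itself, so children whose growth nearly stops can drop out of the growth summaries

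*Protocol*

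**What the plan says.** Protocol 4.1 names a secondary objective of comparing liraglutide with placebo on "Growth velocity (if subject is still growing"). Protocol 4.2 lists growth velocity and height velocity SDS at weeks 26 and 52 under the same condition and adds: "A growth velocity < 1.0 cm/year is defined as no longer growing". Protocol 17.4.3 and SAP 2.2.3 and 3.6.3 repeat the rule. The SAP entry reads "Growth (height) velocity in cm/year and height velocity SDS (if subject is still growing"). It carries an asterisk, explained in the footnote as "Key secondary endpoint prospectively selected for disclosure (e.g. clinicaltrials.gov and EudraCT").

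SAP 3.6.3 calculates height velocity as current height minus baseline height, divided by the days between and multiplied by 365. SAP 3.2 takes baseline from the randomisation visit, with the screening value as fallback. SAP 3.6.3 keeps height velocity SDS at week 26 for finding outliers only. Safety endpoints are descriptive unless otherwise specified.

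The protocol has a second marker of completed growth. Section 8.7.7 states: "An x-ray of left hand and wrist will be performed at Visits 7 and 25 for all subjects for evaluation of bone age". Repeat x-rays are omitted "for subjects for whom the bone age assessment at Visit 7, or at a later visit, indicates that the epiphyses are fused".

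**The concern.** Selecting subjects on a post-randomisation outcome breaks the comparison that randomisation provides. Here the selecting variable is the endpoint itself. If liraglutide slowed growth, more liraglutide children would fall below 1.0 cm/year and leave the summary, and those remaining would look closer to placebo than the randomised groups are.

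This matters because growth is a specific safety question of the trial. Protocol section 18 assumes that risks match those in adults except for "unforeseen effects on growth and pubertal development". Velocity against placebo is a stated objective and is marked for registry disclosure.

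Three descriptive summaries are affected: velocity at weeks 26 and 52, and velocity SDS at week 52. The 1- and 2-year follow-up carries the same condition but covers only liraglutide-treated subjects, so no between-arm bias arises there.

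**Working it through.** **1. Which value decides status.** Neither document defines a pre-randomisation velocity or a baseline test of still growing. The only available velocity is the one from baseline to the visit being summarised. The condition covers velocity as well as the SDS, because Protocol 4.1 attaches it to growth velocity directly.

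**2. What the cut-off means in centimetres** (SAP formula):
- Week 26: 1.0 × 182/365 = 0.50 cm gained.
- Week 52: 1.0 × 364/365 = 1.00 cm gained.

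A child unfused at Visit 7 who gains 0.4 cm by week 26 has a velocity of 0.4 × 365/182 = 0.80 cm/year. That child is no longer growing for the velocity endpoint, yet still due the week 52 x-ray.

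**3. Size of the masking.** The documents give no mean or SD for velocity, so every input below is an assumption. Let velocity V in growers be gamma with mean m and SD s, so shape k = (m/s)² and scale θ = s²/m. With S_k the survival function for shape k and scale θ, the mean among those retained is E[V | V ≥ 1] = m × S_{k+1}(1)/S_k(1). The visible difference is the placebo value minus the liraglutide value.

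(a) *All growers slowed by 25%, 33% or 50%*, m = 2.5–5 and s = 1.5–2.5 cm/year. Visible/true is 0.834 to 1.000.

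(b) *A fraction q = 10–30% of growers slowed by a proportion f, the rest unaffected*, m = 3–5, s = 1.5–2. The true difference is q × f × m.

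| Slowing f | Visible / true |
|---|---|
| 50% | 0.652–0.993 |
| 60% | 0.530–0.973 |
| 70% | 0.323–0.887 |
| 80% | 0.091–0.514 |
| 90% | 0.001–0.023 |

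Worked example: m = 4, s = 1.5, q = 0.2, f = 0.8.
- True difference: 0.2 × 0.8 × 4 = 0.64 cm/year.
- Placebo: 0.2% fall below 1.0; mean of those retained 4.006.
- Slowed children: mean 0.8, SD 0.3; 77.1% fall below 1.0; mean of those retained 1.226.
- Liraglutide retained share: 0.8 × 0.998 + 0.2 × 0.229 = 0.844, so 15.6% are dropped.
- Liraglutide retained mean: (0.8 × 0.998 × 4.006 + 0.2 × 0.229 × 1.226)/0.844 = 3.855.
- Visible difference: 4.006 − 3.855 = 0.151, or 24% of the true one.
- With 47 per arm (Protocol 17.1) and an assumed 60% (28) growing at baseline, about 28 and 24 children remain.

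(c) *Children who have already finished growing.* Protocol 6.3 allows many older subjects: "Proportion of subjects above 14 years of age will be restricted to a total of 70% of randomised subjects". Assume 20–60% have finished, at 0.3 cm/year in both arms, and growers slow by 25–50% (m = 3–5, s = 1.5–2). The present filter shows 0.870–1.000 of the effect in growers. A table of all subjects shows 1 − p, where p is the finished share: 0.40–0.80. A set defined by baseline fusion shows 1.00 if every unfused child is a grower.

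**4. A different model.** With normal velocities (mean 2–5, SD 1.5–2.5) and a fixed slowing of 0.5–2.0 cm/year, 37–95% of the true difference is visible, and exclusion is always higher in the slower-growing arm. With mean 3, SD 2 and slowing 1.0, about 16% of placebo and 31% of liraglutide subjects are dropped, and the visible difference is 0.56.

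**The case against.** The strongest reply is that exclusion is inferred. The documents attach a label and a condition; no sentence says that children below 1.0 cm/year are left out of a table, or at which visit status is judged. That is true and limits confidence. But an endpoint assessed only if the subject is still growing, with that status defined by velocity, leads to exclusion when followed as written, and the SAP's list of changes from the protocol does not alter it.

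Second, other measures remain. Height SDS at weeks 26 and 52 uses the same heights, has no growth condition and is also marked for disclosure. Bone age, Tanner stage, IGF-1 and IGFBP-3 are not conditioned on velocity either. This stands: a growth signal would not be lost altogether.

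Third, the large figures need near-arrest of growth in a subgroup, which nothing in the documents suggests; the 5-week paediatric trial found no evidence of hormonal disruption. That is fair, though five weeks says little about growth over a year. General slowing gives only modest masking in the gamma model, and the size depends on the model chosen.

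Fourth, the filter does useful work, because finished growers dilute an all-subjects table. Item (c) confirms this, and it is why simply deleting the filter is not the answer.

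Fifth, unfused is not the same as growing. If a share u of unfused children have nearly stopped, the baseline-defined set shows 1 − u of the effect: 0.90 at u = 10%, 0.70 at 30%. Above 13% (1 − 0.870) that is below the present filter's worst case in (c). This stands as a limit, but it is dilution that does not depend on treatment, whereas the present rule selects on the outcome.

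**Conclusion.** The concern holds. As written, the rule selects children on the on-treatment value being summarised and would tend to understate any slowing of growth on liraglutide. It should be corrected, but it does not threaten the trial's main conclusions: three descriptive safety summaries are affected and no test is.

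The true size is unknown. It is modest under general proportional slowing in the gamma model (83–100% visible), larger under a fixed slowing in the normal model (37–95%), and severe only if a subgroup falls below 1.0 cm/year (9–51% visible at 80% slowing, 0.1–2% at 90%). In that last case a count by arm would show what the mean hides: 0.2% against 15.6% in the example. Confidence is medium, because leaving these children out is the plain reading and not an explicit instruction.

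**What to change.** Define still growing once, at baseline, as epiphyses not fused on the Visit 7 bone-age x-ray. Keep every such subject with height data in the velocity summaries at weeks 26 and 52 and in the week 52 velocity SDS summary, whatever the later velocity. Within that group, report by arm the number below 1.0 cm/year as an outcome. Show velocity for all subjects, and for those without a readable Visit 7 x-ray, only as a supplementary table or listing. If leaving children out was never intended, the SAP should say so.

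The cost is minor wording in the protocol and SAP and a few table rows. No new assessment is needed: the x-ray is planned for all subjects, and fusion must already be judged to apply the repeat x-ray rule, though the SAP should confirm that it is available as an analysis variable. Velocity SDS may need a floor for very low values.

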5.1 Type of trial

This is a multi-centre 26 week randomised double-blind, parallel-group, placebo-controlled clinical trial followed by a 26 –week open-label extension in subjects aged 10 -17 years with type 2 diabetes. Subjects will be randomised 1:1 to receive liraglutide or liraglutide placebo in combination with metformin with or without basal insulin treatment. Subjects will be stratified at randomisation by sex and according to their age at end of treatment (with two levels: 1: ≤ 14 , 2: > 14 years of age; ≤ 14 years of age is defined as not reaching 14 years and 11 months at the end of treatment (52 weeks)).

The trial consists of a 2 weeks screening period where all screening parameters are assessed. Screening is followed by 11 to 12-weeks run-in period starting at Visit 2 (3 to 4 weeks metformin titration and 8 weeks metformin maintenance). After the run-in period subjects will, if fulfilling the randomisation criteria, be randomised to either liraglutide or liraglutide placebo treatment for 26 weeks. Subjects already treated with a stable dose ≥ 2000 mg of metformin or more for at least 56 days at the time of screening may skip the run-in period and advance directly to randomisation. Subjects who are treated with basal insulin should in addition to the stable dose of metformin have a stable dose of basal insulin for at least 56 days to advance directly to Visit 7.

At the end of the 26 weeks blinded treatment period, the treatment allocation will be unblinded and subjects will continue in a 26 weeks open-labelled treatment period. All subjects will attend a follow-up visit one week after end of treatment.

Further for subjects experiencing confirmed hyperglycaemia according to rescue criterion no. 1 (see section [6.5](#)) rescue treatment will be allowed. Subjects on rescue treatment will remain in the trial.

Subjects receiving rescue treatment should continue to follow the trial schedule for the remainder of the trial.

The maximum duration of the trial including screening and one week follow-up will be up to 67 weeks.

Subjects treated with liraglutide (active treatment) for more than 3 months will be asked to return one and two years after the end of the open label phase of the trial (after trial drug cessation at week 52).

The trial design is shown schematically below in [Figure 5-1](#).

[figure not shown]

Figure 5–1 Trial diagram

- 1) Screening prior to metformin titration
- 2) Run-in: metformin titration to 2000 mg daily if possible or maximum tolerated dose (MTD) ≥ 1000 mg and ≤ 2000 mg after verification of eligibility according to the inclusion and exclusion criteria. Subjects already treated with a stable dose ≥ 2000 mg of metformin or more for at least 56 days at the time of screening may skip the run-in period and advance directly to randomisation. Subjects who are treated with basal insulin should in addition to the stable dose of metformin have a stable dose of basal insulin for at least 56 days to advance directly to Visit 7.
- 3) Randomised treatment: Escalation of liraglutide in 0.6 mg increments over 2-3 weeks to 1.8 mg if possible or MTD. Subjects on basal insulin will have their insulin dose decreased by 20% at randomisation.
- 4) All subjects will be unblinded at Visit 17. Subjects treated with liraglutide will continue with unchanged doses of metformin \pm basal insulin and their treatment with liraglutide. Subjects treated with liraglutide placebo will discontinue liraglutide placebo and will continue on metformin \pm basal insulin.
- 5) All subjects will complete the Visit 26. Subjects treated with liraglutide for more than 3 months will complete Visits 27 and 28.

5.2 Rationale for trial design

A randomised double-blind design was chosen for the efficacy endpoints in order to limit the bias in the conduct and interpretation of the trial. An effect on HbA_{1c} as well as durability effects should be seen by 26 weeks²³. Stratification has been implemented in order to avoid bias arising from gender

and age at end of treatment (≤ 14 and > 14 years of age) (see section [5.1](#) for definition of ≤ 14 years of age).

Subjects' treatment allocation will be unblinded after 26 weeks in order to enable discontinuation of the liraglutide placebo injections which are considered a burden to the children and adolescents.

The current standard of care for this population is metformin treatment or insulin if needed. Subjects will, in order to ensure adequate treatment, be treated with metformin at a dose ≥ 1000 mg and ≤ 2000 mg, throughout the trial. This metformin dose is generally approved for children and adolescents. Subjects entering the trial on a dose of metformin > 2000 mg will be allowed to remain on that dose.

The 26 weeks open label extension has been added in order to assess the safety of liraglutide treatment in the paediatric population. The 2 years follow-up for subjects treated with liraglutide for more than 3 months is added in order to assess any potential long time effect on growth, pubertal development and general safety.

A rescue criterion has been implemented in order to attempt to improve retention in order to obtain additional safety information, and to mimic what would likely occur in clinical practice.

